### 7.3 Exploratory Analyses

#### Log Reductions:

Log10 reductions for analysis of efficacy will be calculated by subtracting the post-test material application log10 recovery from the Treatment Day baseline log10 recovery. Log10 reductions will be calculated for all study materials for both the inguen and the abdomen at each sample time.

The following descriptive statistics for log10CFU/cm^2 and log10CFU/cm^2 reductions will be computed for both the mITT and Per Protocol populations for each test material tested, grouped by anatomical site and each post application sampling time points (30 seconds, 10 minutes and 6 hours): mean, median, standard deviation, minimum, maximum and sample size.

Log10 reductions will be compared between test materials by an Analysis of Variance (ANOVA). In the ANOVA model, the response is the log10 reduction and the predictors are treatment and time point as well as the interaction between treatment and time point. The average difference in log reduction between treatments per time point will be estimated. However, all conclusions for the treatment effect (difference between treatments in log10 reduction) will be based on the primary analysis only.

#### Microbial Baseline Effects:

Additional analyses may be conducted using the same methods as for the primary and secondary analysis using the Per Protocol data set, but with modified baseline requirements to determine the effect of baselines on the outcomes.

Product Expression: The weight (grams) of drug product solutions applied to a treatment area will be estimated as:

Product weight prior to treatment (g) – Product weight post-treatment (g)

Descriptive statistics will be generated for expressed products, and will include: mean, median, standard deviation, minimum, maximum and sample size for each test material. An analysis of variance (ANOVA) will also be performed on the expressed volumes to determine whether the treatments had similar volumes applied. Differences between groups, if found to be significant, will be examined by performing additional follow up tests. The analysis will be based on the mITT / Per Protocol data.

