## 2.0 OBJECTIVE

The primary objective of this study is to compare the immediate antimicrobial properties of octenidine dihydrochloride [OCT] in isopropyl alcohol - clear in a single-use applicator and octenidine dihydrochloride [OCT] in isopropyl alcohol - tinted in a single-use applicator to a Negative Control and an FDA NDA-approved Active Control. Single use applicators filled with 0.9% saline will serve as the Negative Control and Chloraprep® – Hi-Lite Orange® applicator will serve as the Active Control. In agreement with the Food and Drug Administration Tentative Final Monograph (TFM) for *Effectiveness Testing of a Patient Preoperative Skin Preparation*, a log10 reduction study will be used to determine antimicrobial efficacy based on the statistical analyses outlined in published letters from the FDA on January 19, 2017. The updated analysis applies a non-inferiority requirement of the investigative product to an FDA NDA-approved control with a 0.5 log10 margin and a 1.2 log10 superiority requirement over a Negative Control. The average treatment effect of the investigative products compared to the Active and the Negative Controls will be determined from a linear regression of post-treatment log10 bacterial counts after correcting for pre-treatment log10 bacterial loads. The secondary objective is to determine the persistent antimicrobial activity of the two Investigative Products, Active Control, and the Negative Control. Log10 bacterial counts at 6 hours for each treatment site will be converted to a binary (yes or no) success measure with success defined as having skin flora counts that are less than or equal to the baseline skin flora counts. The objective is to demonstrate a success proportion  $\geq 95\%$  on both the abdomen and the inguen with 95% confidence.

Testing will be performed according to the procedures outlined in the Food and Drug Administration Tentative Final Monograph (TFM) for *Effectiveness Testing of a Patient Preoperative Skin Preparation* (FR 59:116, 17 June 94, pp. 31450-31452). The test methods for this evaluation will be based on ASTM Standard Test Method E1173-15,

*Evaluation of Preoperative, Precatheterization, or Preinjection Skin Preparations and the test criteria from the deferral letters published by the FDA on January 19, 2017.*

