#### Product Expression Volumes:

The weight (grams) of drug product solutions applied to a treatment area will be estimated as:

Product weight prior to treatment (g) – product weight post-treatment (g)

The following descriptive statistics for expression volumes will be computed for each product tested at each anatomical site: mean, median, standard deviation, minimum, maximum, and count. An analysis of variance (ANOVA) of the applied volumes will be performed separately for each body site to determine whether the test materials had similar volumes applied. If a significant difference is found, differences between groups will be examined by appropriate follow up tests. Analysis for product expression volumes will be based on the mITT data / Per Protocol data.

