#### Negative Control (not pre-filled):

- 1) Pipette three (3) mL of sterile saline into a suitable sized sterile Petri dish.
- 2) Weigh the Petri dish containing saline and empty applicator including packaging.
- 3) Remove empty applicator from sterile pouch without touching sponge tip.
- 4) Immediately prior to application, dip the applicator sponge in the saline, soaking up as much of the solution as possible.
- 5) Carefully turn the applicator head up and then position the applicator over the treatment area (above the skin). Once in position, carefully turn the applicator head down and place the applicator sponge onto the treatment area.
- 6) Post-treatment, re-weigh the Petri dish and applicator including packaging.
- 7) Retain the label from the applicator package, discard the used applicator and Petri dish.

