3.4 Endpoints

- Primary Endpoints
 - Log CFU/cm² of skin for each treatment per body site per time point.
- Secondary Endpoints
 - Responder rates will be calculated by converting each log₁₀ CFU/cm² reduction at 6 hours post-treatment time point to a binary (yes or no) success measure. Success at 6 hours post-treatment time point is defined as having skin flora counts that are less than or equal to the baseline skin flora counts on both body sites.
- Exploratory Endpoints
 - Log₁₀ CFU/cm² reductions from baseline for each treatment per body site per post-application time point.
 - Product expression volumes: the weight of the treatment applied to a test site will be estimated by subtracting the weight measurement (g) of the treatment after the application from the weight of the treatment (g) before application.
- Safety Endpoints
 - Skin irritation scores (Erythema, Edema, Rash and Dryness scores for each time point)

4 Sample Size

A sufficient number of volunteers will be enrolled in the screening phase such that the total numbers of evaluable samples collected from groin and abdominal regions are not less than 36 evaluable test sites from each treatment arm (minimum of 144 each for groin and abdominal regions). A minimum of 72 evaluable subjects is required to achieve a total of at least 144 test sites for groin and abdominal regions. Subjects must satisfy all Screening Day and Treatment Day Inclusion/Exclusion Criteria prior to screening sample collection and Treatment Day procedures. If the required numbers of subjects do not qualify from the initial screening group, additional volunteers will be recruited.

This is a Phase II study to assess the immediate and persistent antimicrobial effect of the Investigational Products relative to the Negative Control and the Active Control using a log₁₀ reduction study (i.e., average treatment effect) according to the procedures outlined in the Food and Drug Administration Tentative Final Monograph (TFM) for Effectiveness Testing of a Patient Preoperative Skin Preparation (FR 59:116, 17 June 94, pp. 31450-31452) and the test criteria outlined in the deferral letters from the FDA published on January 19, 2017. The purpose is to inform design of future efficacy studies, therefore no sample size calculation was performed to provide statistically-powered evidence of efficacy as part of this study. The sample size is deemed adequate for these purposes.

5 Intended Statistical Software

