7.3.3.3 Product Expression Volumes/Weight

An analysis of variance (ANOVA) of the applied volumes/weight will be performed separately for each body site based on mITT data and/or per-protocol data. In the model, there will be a random subject effect, a fixed body side (left or right) effect, a fixed treatment effect and the interaction between fixed effects. ANOVA table will be checked to see whether the treatment has a significant effect on product expression volumes as well as the interaction. If a significant difference is found, subgroup comparisons with Tukey’s method will be made to determine which pair of comparisons shows significant difference.

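### The exploratory check for similar applied volumes is run on grams, so it is not valid for volume contrasts between the saline control and the alcohol-based products

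*Protocol*

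**What the plan says.** Protocol 7.3 (Product Expression) and 15.3 (Product Expression Volumes) define the measurement in the same way: "The weight (grams) of drug product solutions applied to a treatment area will be estimated as" the weight before treatment minus the weight after. Both sections then treat the result as a volume. In 7.3, "An analysis of variance (ANOVA) will also be performed on the expressed volumes to determine whether the treatments had similar volumes applied". In 15.3 the ANOVA is run separately by body site, "to determine whether the test materials had similar volumes applied".

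The SAP keeps the mixture. Section 3.4 lists product expression volumes among the exploratory endpoints but defines them by subtracting weights in grams, and 7.1.4 repeats the subtraction. In 7.3.3.3, "An analysis of variance (ANOVA) of the applied volumes/weight will be performed separately for each body site", with a random subject effect, fixed side and treatment effects and their interaction, and Tukey comparisons if a significant difference is found. Neither document gives a density or a conversion to mL.

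The Negative Control is part of this analysis. Protocol 13.6 has all test materials weighed before and after application, Appendix 1 gives a weighing procedure for saline, and SAP Tables 3 and 4 list treatment D under product expression volumes. Protocol 8.0 gives 70% v/v isopropyl alcohol as the vehicle of both Investigational Products and of the Active Control; the Negative Control is 0.9% saline.

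**The concern.** Weight stands in for volume only when the liquids have the same density. Within the three alcohol-based products that is nearly so. Against saline it is not. A comparison in grams can then go wrong in two ways. Equal volumes can be reported as a treatment difference, and a real shortfall in the saline volume can be reported as similarity.

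The saline arm is where a true difference in delivery is most plausible. The antiseptics come in 3 mL single-use applicators. For saline, Appendix 1 has staff "dip the applicator sponge in the saline, soaking up as much of the solution as possible". The documents describe no other comparison between arms of the amount applied. What is at stake is whether the study can report correctly on how evenly its control was delivered, which is useful in a trial meant to inform later designs. No efficacy conclusion is at stake.

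**Working it through.** **Inputs from the documents.** There are 72 evaluable subjects with two sides each (Protocol 11.1), allocated as 12 subjects to each of six treatment pairs (SAP 3.3). Alpha is 5%, two-sided (SAP 7.3).

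**Reproducing the plan's figure.** Sites per material per region = 72 × 2 / 4 = 36. Each material appears in 3 of the 6 pairs, so 3 × 12 = 36. Both agree with SAP Table 1.

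**Assumed inputs.** The documents give no density, expected applied weight or standard deviation (SD) for product expression. I take saline at 1.000 to 1.005 g/mL (1.005 in the central case) and 70% v/v isopropyl alcohol at 0.85 to 0.89 g/mL (central 0.877). Variability is shown over a range of CVs.

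**Gap in grams at equal volume** = d(saline) / d(alcohol) − 1.
- Central: 1.005 / 0.877 − 1 = 14.6%. For 3 mL that is 3.02 g against 2.63 g.
- Lowest: 1.000 / 0.89 − 1 = 12.4%.
- Highest: 1.005 / 0.85 − 1 = 18.2%.

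**Saline shortfall by volume that gives equal grams** = 1 − d(alcohol) / d(saline).
- Central: 1 − 0.877 / 1.005 = 12.7%.
- Lowest: 1 − 0.89 / 1.000 = 11.0%.
- Highest: 1 − 0.85 / 1.005 = 15.4%.

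**Chance of falsely flagging equal volumes.** I approximate the SAP model by a one-way ANOVA with four groups of 36; the random subject effect is left out because no variance components are given. Per mL applied, the mean weights are 0.877, 0.877, 0.877 and 1.005 g, with overall mean 0.909. The sum of squared deviations is 3 × 0.032² + 0.096² = 0.012288. The noncentrality is λ = 36 × 0.012288 / SD² = 0.4424 / SD², with SD = CV × 0.877 common to all arms. The critical value of F(3, 140) at 5% is 2.67.

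| CV | SD (g per mL) | λ | Probability of rejection | Same, alcohol density 0.89 to 0.85 |
|---|---|---|---|---|
| 20% | 0.1754 | 14.4 | 90% | 80% to 98% |
| 30% | 0.2631 | 6.4 | 53% | 43% to 75% |
| 40% | 0.3508 | 3.6 | 32% | 25% to 48% |

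A simulation of 4,000 trials, with the saline SD in grams scaled up by its density, gave somewhat lower values at central density: 85%, 49% and 28%.

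**Chance of seeing a real 12.7% saline shortfall.** In the same simulation the ANOVA on grams rejected in 4.7% to 5.2% of trials at CVs of 10% to 40%. That is its nominal level, because the mean weights are then equal. The same data expressed in mL were flagged in 84%, 46% and 26% of trials at CVs of 20%, 30% and 40%.

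**The case against.** The strongest reply is that little depends on this check. It is exploratory in both documents, it feeds no success criterion, covariate or exclusion, and a significant result leads only to follow-up comparisons. That is correct, and it sets the severity.

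A second reply is that the unit is open to view: every definition says weight, and the SAP heading couples volumes with weight. With descriptive statistics planned for each material, a reader who knew the densities could convert the arm means. That stands as mitigation. It does not make the planned test a test of volume, and the protocol still states a conclusion about volumes.

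Third, dividing by density is not exact. The used alcohol applicator is re-weighed after treatment, so any alcohol that has evaporated by then counts as applied. This adds to the apparent alcohol weight and could offset part of the gap in grams. Its size is not given, so a volume in mL would be approximate.

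Three stronger readings are tempting, and the documents do not support them.
- That equal volumes are bound to test as different. This depends on the variability between sites, which is not given; at a CV of 40% the probability is only about 32%.
- That a hidden saline shortfall would inflate NC − IP against the 1.2 log10 criterion. No passage links applied volume to counts. Appendix 1 sets the same scrub times for all materials and requires the area to be completely wetted, and nothing shows that dipping under-delivers.
- That the whole check fails. The two Investigational Products and the Active Control share the 70% v/v alcohol vehicle, so their contrasts with one another are nearly unaffected.

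**Conclusion.** The point holds for contrasts with the Negative Control only. A test stated to show similar volumes is run on unconverted grams across liquids of different density, and both documents do this. Under the assumed densities, a saline shortfall of about 11% to 15% by volume would leave the grams equal and go undetected. Equal volumes would differ by about 12% to 18% in grams and might be falsely flagged, very probably at a CV of 20% and about as often as not at 30%. The percentages rest on densities and variability that are not in the documents, and the rejection probabilities also on a one-way approximation. That grams cannot serve as volume across these liquids needs only that their densities differ. Severity is low: the result could mislead a description of product delivery, but it reaches no efficacy conclusion.

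**What to change.** In SAP 7.1.4 and Protocol 7.3 and 15.3, define expressed volume (mL) as the weight difference (g) divided by the density of that material. Run the SAP 7.3.3.3 ANOVA and Tukey comparisons on mL and keep grams as a descriptive listing. Add a sentence that the mL value is approximate, because alcohol lost to evaporation before re-weighing counts as applied. The cost is one formula and a density for each of the four materials; no new clinical measurement is needed.

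At minimum, state that the check compares weight, and limit any conclusion about volume to the three alcohol-based products.

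A separate matter to reconcile: Protocol 2.0 says "Single use applicators filled with 0.9% saline will serve as the Negative Control", whereas Protocol 8.0 has empty applicators supplied for this arm and Appendix 1 describes dipping one that is not pre-filled. The density argument does not depend on how that is settled.

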### 7.4 Sample Size Justification

This is a Phase II study to assess the immediate and persistent antimicrobial effect of the Investigational Products relative to the Negative Control and the Active Control using a log10 reduction study according to the procedures outlined in the Food and Drug Administration Tentative Final Monograph (TFM) for *Effectiveness Testing of a Patient Preoperative Skin Preparation* (FR 59:116, 17 June 94, pp. 31450-31452) and the test criteria outlined in the deferral letters from the FDA published on January 19, 2017. The

purpose is to inform design of future efficacy studies, therefore no sample size calculation was performed to provide statistically-powered evidence of efficacy as part of this study. The sample size is deemed adequate for these purposes.

## 7.5 Safety Analysis

The full Intent-to-Treat data set (all randomized subjects) will be used for the safety analysis. The principal measures of safety will be skin irritation scores and the incidence of adverse events reported during the study.

Differences between both Investigational Products, Active Control, and Negative Control will be evaluated on skin irritation data.

## 7.6 Study Flow Chart

Procedure	Timeline (Days)			
	14 or more prior to Baseline	3 or more prior to Baseline	0 Baseline	Treatment Day 3 or more post Baseline
Informed Consent Obtained	X			
Product-Restriction Period	X	X	X	X
Inclusion/Exclusion Criteria including Medical History Reviewed	X	X	X	X
Clipping Hair From Test sites		X		
Baseline Screening			X	
Test-Day Baseline Sample				X
Product Application				X
30-Second Post-Product Application Sample				X
10-Minute Post-Product Application Sample				X
6-Hour Post-Product Application Sample				X
Adverse Events		X	X	X

**Note:** Visual evaluations of the skin on each test area will be performed at each laboratory visit prior to treatment, and prior to 30-second, 10-minute, and 6-hour post-treatment microbial sampling.

**Note:** All sampling times will be calculated from the completion of the dry time of each product following application.

## 8.0 TEST MATERIALS

The test materials (Investigational Products, Active Control, and empty applicators for

the Negative Control) to be used in this evaluation will be supplied by the Study Sponsor. The test materials will be supplied as individually packaged sterile single-use applicators. BSLI will provide sterile 0.9% saline for use with the empty Negative Control applicators. Due to visual differences between each of the test materials, the products cannot be fully blinded. The products will be coded as follows:

Product Code	Study Product
A, B or C	Investigational Product #1 – Octenidine Dihydrochloride in Isopropyl Alcohol in a single-use applicator - clear
A, B or C	Investigational Product #2 – Octenidine Dihydrochloride in Isopropyl Alcohol in a single-use applicator - tinted
A, B or C	Active Control – Chloraprep® - Hi-Lite Orange® applicator
D	Negative Control – sterile 0.9% saline applied with single use applicator

The test materials will be received and stored by BioScience Laboratories, Inc. (BSLI) in accordance with instructions from the Sponsor and BSLI procedures and retained in secure quarantine when not being used in testing. BSLI will maintain an inventory of the test materials retained in secure quarantine when not being used in testing, and a log of use. Unused, sealed test materials will be stored by BSLI until the Sponsor specifies its disposition. In the absence of a disposition request from the Sponsor within 1 year of planned usage, the test materials will be returned to the Sponsor. No test materials will be destroyed unless requested by the Sponsor. Blinded Lot Numbers and Expiration dates will be provided by the Sponsor with each product shipment. The unblinded lot numbers of the Investigational Products and Active Control will be provided to BSLI by the Sponsor at the completion of the study when unblinding has occurred.

Investigational Product #1 (IP1): Octenidine Dihydrochloride in Isopropyl Alcohol in a 3 mL single-use applicator - clear

Active Ingredient: 0.4% w/v Octenidine Dihydrochloride / 70% v/v Isopropyl Alcohol (IPA)

Lot Number: \_\_\_\_\_

Expiration Date: \_\_\_\_\_

Investigational Product #2 (IP2): Octenidine Dihydrochloride in Isopropyl Alcohol -  
in a 3 mL single-use applicator with tinted pledget  
[REDACTED]

Active Ingredient: 0.4% w/v Octenidine Dihydrochloride (OCT) / 70%  
v/v Isopropyl Alcohol (IPA)

Lot Number: \_\_\_\_\_

Expiration Date: \_\_\_\_\_

Active Control (AC): ChloraPrep® 3 mL Hi-Lite Orange® applicator

Active Ingredient: 2% w/v Chlorhexidine Gluconate (CHG) / 70% v/v  
Isopropyl Alcohol (IPA)

Lot Number: \_\_\_\_\_

Expiration Date: \_\_\_\_\_

Negative Control (NC): Sterile 0.9% Saline applied with single-use  
applicator

Active Ingredient: Not Applicable

Lot Number: \_\_\_\_\_

Expiration Date: \_\_\_\_\_

**9.0 LABORATORY SUPPLIES AND EQUIPMENT (provided by BioScience Laboratories, Inc.)**

**9.1 Equipment**

The equipment used during this study will be detailed on Clinical Trials Equipment Tracking Forms, and the forms will be included in the Final Report.

**9.2 Supplies**

The supplies used during this study will be detailed on Clinical Trials Supplies Tracking Forms, and the forms will be included in the Final Report.

**9.3 Media**

Sampling Fluid

Sterile Sampling Solution (SS):

[REDACTED]

Diluting Fluid

Butterfield's Phosphate Buffered Water (PBW):

312  $\mu\text{M}$   $\text{KH}_2\text{PO}_4$ , pH  $7.2 \pm 0.1$

#### Solid Media

Tryptic Soy Agar with product neutralizers (TSA+) – may be purchased or made by BSLI

### **10.0 NEUTRALIZATION**

A neutralization study will be performed on the abdominal region of at least 12 subjects, to ensure that the neutralizers used in the recovery medium quench the antimicrobial activity of the three test materials, and that the neutralizers are not toxic to the bacteria. *Staphylococcus epidermidis* MRSE (ATCC #51625) and *Staphylococcus epidermidis* (ATCC #12228) will be used as the challenge species in the neutralization study. The neutralization study will follow guidelines based on ASTM E1054-08(2013), *Standard Test Methods for Evaluation of Inactivators of Antimicrobial Agents*. Reference Appendix 3 of this Protocol for specific guidelines for the Neutralization Assay. The neutralization validation will be completed prior to initiation of the clinical investigation and results will be documented in the Final Report.

